4.2.6.1. Pre-Training

Studies have shown that pre-training significantly improves the performance of the model. For example, Bagad et al.⁴⁰ found 17% improvement in area under the curve (AUC) when using a pre-trained model compared to one without pre-training. This is particularly important when dealing with small (<1000 samples) or medium size data (<10,000 samples). Therefore, we may use this approach. For example, one way of pre-training the model is to classify “mm” vs “ah” using the data from participants that were negative at both swab #1 and swab #2. Using transfer learning the weights of this model can be used for a sick vs. well classifier¹⁹. Other pre-training approaches will be considered.

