3. ANALYSIS SETS (POPULATIONS FOR ANALYSIS)

Data for all participants will be assessed to determine if participants meet the criteria for inclusion in each analysis population prior to releasing the database and classifications will be documented per standard operating procedures.

Algorithm Population	Description
Full Analysis Set (FAS) as per the Main SAP	All participants who sign the informed consent document and enroll in the study, as defined in the main SAP. Qualified participants are males or females aged 18 years and older (or the minimum state-specific age of consent if > 18) at Screening visit, who are willing and able to comply with daily symptom and voice assessments on the Electronic Diary application and other study procedures including self-collection of nasal swabs, are expected to be available for the duration of the study, and are capable of giving informed consent.
Primary Analysis Set	Participants in FAS who have a negative RT-PCR test (at swab #1) and no acute symptoms (as determined by the enrollment questionnaire), and who become positive for SARS-CoV-2, influenza virus, or RSV (at swab #2) and symptomatic during the study.
Secondary Analysis Set A	Participants in FAS who have a negative RT-PCR test (at swab #1) and a negative RT-PCR test (at swab #2) irrespective of symptoms.
Secondary Analysis Set B	Participants in FAS who have a positive SARS-CoV-2, influenza virus, or RSV RT-PCR test (at swab #1) and are symptomatic.
CCI [REDACTED]	[REDACTED]

For the purpose of algorithm development and testing, the sick and well states are defined for each of the analysis sets (when applicable).

For Primary Analysis Set

The **sick state** is defined by considering a window of Electronic Diary data around a positive RT-PCR test at swab #2.

To determine the start of the sick state window, consider the difference in symptoms between consecutive recordings. The start of the sick window will be a symptom increase within 3 days prior to swab 2. If there is no symptom increase within these 3 days, the start of the window will be on swab #2 day.

If the number of days between swab #1 and swab #2 is less than or equal to 3, the sick state window will start on swab #2 day.

The *end of the window* is after swab #2 and defined by either:

- a. The last time the total symptom score is above 40% of the maximum total symptom score, or
- b. The final available datapoint if the total symptom score stays above 40% of the maximum score.

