- Analysis time window from 8 days before swab #1 up to 8 days after swab #1
- Analysis time window of 8 days up to and including swab #2.

This well and sick data will serve as the input to the machine learning and deep learning analysis, and the models will be trained, validated and tested as described in [Section 4.2.5](#) and [Section 4.2.6](#).

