5.5. Further Model Testing

5.5.1. Model Testing on RT-PCR Negative Participants

- Analysis Set: Participants in Secondary Analysis Set A to test models trained on the Primary Analysis Set ([Section 3](#)).
- Statistical Method: (a) As listed in [Section 4.6](#)., the best-performing output model from the classical machine learning ([Section 4.2.5](#)), deep learning ([Section 4.2.6](#)), fusion method ([Section 4.3](#)) and well vs. sick analysis with sick state definition centered around maximum total symptom score method ([Section 4.4](#)) will be tested on negative cases to estimate the false positive rate of the models. (b) The best performing Change From Baseline model will also be tested on analysis set above.
- Summaries: The following results will be generated for the specified analysis set (data permitting):
 - Confusion matrix will be tabulated and a listing of the performance measures provided for the two models (a) and (b).
 - Table of values of *specificity* as a function of Total Symptom Score thresholds for both models.
 - Plot of *specificity* against Total Symptom Score thresholds for both models.

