5.5.2. Model Testing on Positive Symptomatic Participants at Swab #1

- Analysis Set: Participants in Secondary Analysis Set B ([Section 3](#)) to test model trained on the Primary Analysis Set.
- Statistical Method: As listed in [Section 4.6](#)., the best-performing output model from the classical machine learning ([Section 4.2.5](#)), deep learning ([Section 4.2.6](#)), fusion method ([Section 4.3](#)) and well vs. sick analysis with sick state definition centered around

maximum total symptom score method (Section 4.4.) will be tested on participants who are positive and symptomatic at swab #1 as an independent test set.

- Summaries:
 - Confusion matrix will be tabulated and a listing of the performance measures provided.
 - Table of values of *sensitivity* as a function of Total Symptom Score thresholds.
 - Plot of *sensitivity* against Total Symptom Score thresholds.

CCI [Redacted]

[Redacted]

[Redacted]

[Redacted]

CCI [Redacted]

[Redacted]

[Redacted]

[Redacted]

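### The plan does not guarantee that the further-testing participants stay out of model building: the example pre-training source is Secondary Analysis Set A, and adSAP 4.4 can be read as training on all three swab groups

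*SAP*

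**What the plan says.** All references are to the algorithm development SAP (adSAP, Appendix A of the SAP).

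- **4.2.6.1 Pre-Training.** Pre-training is optional: "Therefore, we may use this approach". The one worked example is a task separating two phonemes, "using the data from participants that were negative at both swab #1 and swab #2". The section then says: "Using transfer learning the weights of this model can be used for a sick vs. well classifier". It adds that other approaches will be considered.
- **Section 3, Analysis Sets.** Set A is "Participants in FAS who have a negative RT-PCR test (at swab #1) and a negative RT-PCR test (at swab #2) irrespective of symptoms". Set B is "Participants in FAS who have a positive SARS-CoV-2, influenza virus, or RSV RT-PCR test (at swab #1) and are symptomatic".
- **4.4.** Sick or well windows are defined for three groups: negative then positive, positive at swab #1, and negative at both swabs. The section closes: "This well and sick data will serve as the input to the machine learning and deep learning analysis, and the models will be trained", and goes on to validation and testing.
- **5.3.** The analysis set for the 4.4 analysis is the Primary Analysis Set.
- **4.6 and 5.5.1.** The false-positive rate is estimated on negative cases, using "Participants in Secondary Analysis Set A to test models trained on the Primary Analysis Set".
- **5.5.2.** Set B also tests a model trained on the Primary Analysis Set, and is described "as an independent test set". The plan uses that phrase for Set B only.

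**The concern.** A test set gives an honest estimate of performance only if its members played no part in building the model. Two passages leave that open.

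First, if the example pre-training is used, the network's starting weights come from recordings of the same people on whom 5.5.1 later counts false positives. Such a model is not trained only on the Primary Analysis Set, as 5.5.1 assumes. The network could already have adapted to those speakers and their recording conditions.

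Second, if a programmer follows 4.4 to the letter, both-negative and swab #1 positive participants enter training with their sick/well labels and are then scored under 5.5.1 and 5.5.2. For the both-negative group, 4.4 keeps the Section 3 windows, so the same labelled recordings could be fitted and then tested. Set A is taken regardless of symptoms, so training on it would teach the model to call symptomatic negatives well. Section 5.5.1 then reports specificity by symptom-score threshold in those same people.

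At stake are the false-positive estimate, read against the 60% minimum specificity in 4.1, and the additional sensitivity check in Set B.

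**Working it through.** The point concerns data flow, so it is settled by tracing who enters which step.

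**Step 1. Pre-training against 5.5.1.**

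| Step | Participants |
|---|---|
| Example pre-training (4.2.6.1) | negative at swab #1 and swab #2 |
| Set A (Section 3) | negative at swab #1 and swab #2, any symptoms |
| False-positive test (5.5.1) | Set A |
| Stated training source (5.5.1) | Primary Analysis Set |

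The first three rows describe the same people. The splits in 4.2.5.1 (for example 80/20 by subject) and 4.2.6.3 (for example 70/10/20) divide the modelling data. Neither mentions Set A, and no passage removes pre-training participants from 5.5.1.

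**Step 2. How far this route reaches.** Set B is positive at swab #1, so nobody in it is negative at both swabs. Primary Analysis Set members turn positive at swab #2, so none of them is negative at both swabs either. Pre-training therefore cannot touch Set B or the Primary Set hold-out. The classical models of 4.2.5 are not pre-trained. Only pre-trained deep-learning models, and fusion models that use them, are exposed.

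**Step 3. Section 4.4 against 5.3 and 5.5.** The closing sentence of 4.4 names no group, so it covers all three. Section 5.3 restricts the same analysis to the Primary Analysis Set, and 5.5.1 and 5.5.2 say that Sets A and B only test. These statements cannot all be followed. On the literal reading, the example splits would put about 80% of the two extra groups into model building (80% training, or 70% + 10% training and validation).

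**Step 4. Why the further tests carry weight.** First, the plan's own precision figures, from 1.96 × √(0.7 × 0.3 / n):

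- n = 100: 1.96 × √0.0021 = 8.98 points, as stated in 4.1.
- Cases for a 10-point margin: 1.96² × 0.21 / 0.01 = 80.67, so 81, as stated in 4.1.

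With the example 20% hold-out, about 20 of 100 cases remain for the internal test:

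- n = 20: 1.96 × √(0.21 / 20) = 20.1 points.

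The internal test alone is therefore imprecise for sensitivity.

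**Step 5. Price of separating the roles.** The documents give no size for Set A. Assume 500 to 6,000 people, one prediction per person and a true specificity of 60%. The 95% half-width is 1.96 × √(0.6 × 0.4 / m), where m is the number kept for testing.

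| Share of Set A kept for testing | Set A = 500 | Set A = 6,000 |
|---|---|---|
| all | 4.3 points | 1.2 points |
| half | 6.1 points | 1.8 points |
| 20% | 9.6 points | 2.8 points |

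These figures price the remedy. They do not measure bias.

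**The case against.** The strongest reply is that this is a matter of wording. Pre-training is permitted rather than planned, and the population is only an example. Its label is the phoneme, with no sick/well information, and the classifier itself is then trained on the Primary Analysis Set. The windows for the other two groups in 4.4 have a natural purpose, because 4.6 tests the 4.4 model on negatives and on swab #1 positives, and that testing needs windows. Section 5.3 already names the right analysis set. The success criterion in 4.1 is sensitivity, which pre-training on Set A does not put at risk through Set B or the hold-out.

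Most of this stands, and it limits the point. It does not supply the missing exclusion in 4.2.6.1, and it does not tell a programmer which of 4.4 and 5.3 governs.

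A reader might go further and infer three things that the documents do not support:

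- **That the further tests are already compromised.** This depends on whether the optional step is taken and on which reading of 4.4 is coded.
- **That no clean false-positive check would remain.** The Primary Set hold-out also yields specificity (4.2.5.1, 4.2.5.2). In addition, one analysis-set row, part of 4.6 and the material after 5.5.2 are redacted, so what else exists cannot be judged.
- **That pre-training makes specificity optimistic by a known amount.** With a phoneme label, any leak runs through learned speaker and recording features. Neither its size nor its direction can be derived from the documents.

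**Conclusion.** The concern holds in a limited form: independence of the further-testing sets is intended but not secured.

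- **Set A, through pre-training.** If the 4.2.6.1 example is used as written, the pre-training population and the false-positive test population coincide, up to all of Set A. The effect is confined to pre-trained deep-learning or fusion models.
- **Sets A and B, through 4.4.** The literal text contradicts 5.3, 5.5.1 and 5.5.2. This is the only route by which Set B could be affected.

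The conclusion rests on the analysis-set definitions and on the absence of any exclusion rule in the readable text. It needs no numerical assumption. The assumed size of Set A bears only on the cost of the remedy. The change is worth making because it is cheap and removes a conflict that two programmers could resolve differently.

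**What to change.** Make two additions to the adSAP:

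1. In 4.2.6.1, state that any participant whose recordings are used for pre-training is excluded, by subject, from the 5.5.1 test. One way is to reserve a subject-level part of Set A for testing before any modelling starts. An even split is not essential.
2. In 4.4, state that only Primary Analysis Set windows enter training and validation, and that the windows for both-negative and swab #1 positive participants are used for testing only. This brings 4.4 into line with 5.3, 5.5.1 and 5.5.2.

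The cost is two sentences, a recorded subject list, and a somewhat smaller pre-training or false-positive test set. Under the assumed sizes, testing on half of Set A instead of all of it widens the 95% half-width from 4.3 to 6.1 points at 500 people and from 1.2 to 1.8 points at 6,000. No figure stated in the plan changes.

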4.2.6.2. Data Augmentation

A common approach to increase the sample size or balance the data when dealing with imbalanced datasets is to use data augmentation. It has been shown that data augmentation helps to improve the performance of the model^{18,51}. Various data augmentation methods may

be used such as adding gaussian noise to the audio file, pitch shifting, shifting the time signal and stretching the time signal^{18,52}.

4.2.6.3. Deep Learning Model Training and Testing

The dataset will be divided into three separate datasets: training (e.g., 70% of data), validation (e.g., 10% of data) and test set (e.g., 20% of data). We will replicate the training and validation split three times at the subject level to ensure the results are not biased by single randomization. The training of the model requires the choice of an error function, so called a loss function, that can be used to estimate the loss of the model so that the parameters can be updated to reduce the loss on the next evaluation. Given that we have a binary classification problem (sick vs well), our loss function would be binary cross entropy, or weighted binary cross entropy. To optimize the parameters of the model, we will either use ADAM or Stochastic Gradient Descent (SGD) approach. The name ADAM is derived from adaptive moment estimation. ADAM uses momentum of the optimization object and adaptive learning rate to converge faster than SGD⁵³. We will use learning rates such as 0.001 or 0.0001 as the starting point.

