4. GENERAL METHODOLOGY AND CONVENTIONS

4.1. Hypotheses and Decision Rules

Given the algorithm's intended use as a screening tool in the general population not guided by a healthcare professional, we would define the success criteria for the algorithm as achieving a sensitivity on par with that of a rapid antigen test for SARS-CoV-2 infection as observed in real world studies, which is between 60% and 80%¹. Hence, the success criteria for the algorithm will be an observed sensitivity of 70% or better.

The specificity of the algorithm will be assessed with a target minimum specificity of 60% as observed in other studies that use audio signals to detect SARS-CoV-2 infection². The goal is to optimize the sensitivity of the algorithm as the primary performance measure without compromising the minimum specificity, since this algorithm is meant to be used as a screening tool (high sensitivity) and not a diagnostic tool. The reference rapid antigen test benchmarks compared to RT-PCR test for SARS-CoV-2 are as follows¹: sensitivity $\geq 80\%$ in symptomatic individuals and sensitivity $\geq 60\%$ in asymptomatic individuals.

The probability that the observed sensitivity for symptomatic RT-PCR positive participants in AcRIS is greater than 70% with a total number of 100 cases is given in the following table for two assumed true values of expected sensitivity.

Table 1. Probability that observed sensitivity in symptomatic RT-PCR positive participants in AcRIS is greater than 70% with total of 100 cases.

[figure not shown]
True Sensitivity	Probability of Observed Sensitivity > 70% ¹
60%	0.02
75%	0.88
80%	0.99

Thus, with at least 100 symptomatic RT-PCR positive participants in AcRIS, we hypothesize that the study has high probability of success under these conditions.

Furthermore, Figure 1. illustrates the number of cases required to achieve target sensitivity values for a given screening tool – e.g., for a sensitivity of 70% with 10% margin of error for the 95% confidence interval (i.e., 60% to 80%), 81 cases are required (assuming a binomial distribution for the sensitivity values). Identifying 100 symptomatic positive cases should allow us to attain 70% target sensitivity with precision of 8.98%.

¹ Under the assumption of a binomial distribution.

Figure 1. Estimation of the number of cases required to achieve target sensitivity values assuming a 10% margin of error.

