4.2.5.1. Classical Machine Learning Model Training and Testing

The data will be randomly divided into two sets by subject: training (e.g., 80% of subjects) and test set (e.g., 20% of subjects). Repeated stratified k-fold cross validation (on the subject level) on the training data will be used to evaluate performance, as it provides confidence in the resulting performance values. Both k (number of folds) and n (number of repetitions) will be chosen based on the final sample size. The test set will be a hold-out test set until model training and validation is complete.

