4.2.6. Deep Learning

[figure not shown]
In addition to classical machine learning algorithms, deep learning models will be used to perform the binary classification of well versus sick states. The input data for the deep learning models will include spectrograms, Mel-spectrograms, or other variants of spectrogram such as log-Mel-spectrogram or MFCC, as described in [Section 4.2.4](#) for the CNN models or the audio files in case of Transformer models.

Deep learning models have been widely used to classify covid positive and negative participants using voice or cough data (e.g., see review papers by Deshpande et al ³⁵ and Qian et al, ³⁶). Most studies have used various architectures of convolutional neural network (CNN) models, and few have applied recurrent neural networks (RNN) ³⁷. More recently, Transformers have been found useful for speech analysis ^{38,39}. We may apply various architectures of the CNN models such as ResNet18 (Residual Neural Network 18) ⁴⁰, VGG16 (Visual Geometry Group 16) ⁴¹, VGG19 ⁴² or custom built models.

We will choose the CNN architectures based on the dimension of the final dataset. The details of the CNN architectures that may be computed are as follows:

[figure not shown]
ResNet18: ResNet-18 is a convolutional neural network that is 18 layers deep (Figure 2). ResNet is more recent architecture than original CNN architectures like VGG. The advantage of ResNet is the skip connections, or shortcuts to jump over some layers. One of the problems of deep neural networks is that the first layers' weights will not change much during the training process. This is called vanishing gradient. The skip connections solve the problem of vanishing gradients in deep neural networks by allowing this alternate shortcut path for the gradient to flow through. These connections also help by allowing the model to learn the identity functions which ensure that a higher layer will perform at least as well as the lower layer, and not worse. Layers may be added or removed based on our data. Cross-validation will be used to determine if the model is overfitting the training data. In that case, layers will be removed to reduce the complexity of the model. If the model is underfitting the data, more layers will be added.

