5.2. Classification of Well and Sick States Using Deep Learning Models

- Analysis Set: Participants in Primary Analysis Set if deemed appropriate by data.

- Statistical Method: Deep learning modeling will be performed as described in [Section 4.2.6](#). The best performing model will be selected based on performance metrics listed in [Section 4.2.6.4](#).

- Summaries:

Using the output of the best performing model described in [Section 4.2.6.5](#)., the following results will be generated for the specified analysis set (data permitting):

- Listings of the specifications of the spectrograms and mel-spectrograms used for the final deep learning model ([Section 4.2.4](#).)
- Summary statistics of the performance measures listed in [Section 4.2.6.4](#). (mean and standard deviation) for classification of sick and well states for the validation set. Results will be presented in a table.
- The confusion matrix for the test set will be tabulated and a listing of the performance measures provided.

If a fusion model is deemed appropriate by data (as described in [Section 4.3](#).), the following will be generated:

- Listings of the voice features ([Section 4.2.2](#).) and specifications of the spectrograms and mel-spectrograms used for the final model ([Section 4.2.4](#).)
- Summary statistics of the performance measures listed in [Section 4.2.6.4](#). (mean and standard deviation) for classification of sick and well states for the validation set. Results will be presented in a table.
- The confusion matrix for the test set will be tabulated and a listing of the performance measures provided.

5.3. Well vs. Sick Analysis with Sick State Definition Centered Around Maximum Total Symptom Score

- Analysis Set: Participants in Primary Analysis Set ([Section 3](#)) if deemed appropriate by data.
- Statistical Method: Listed in [Section 4.4](#).
- Summaries:

Using the output of the best performing classical machine learning ([Section 4.2.5](#).), deep learning ([Section 4.2.6](#).) or fusion method ([Section 4.3](#).), the following results will be generated for the specified analysis set (data permitting):

- Listing of the features used in the final classical machine learning model and/or Listings of the specifications of the spectrograms and mel-spectrograms used for the final deep learning model ([Section 4.2.4](#).)

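### Three 10% validation splits make deep-learning model selection imprecise; the subject-level k-fold already planned for the classical models would serve better

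*SAP*

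**What the plan says.** All section numbers below refer to the adSAP in Appendix A of the SAP.

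- **Case numbers (4.1).** The planning figure is 100 symptomatic positive cases: "Identifying 100 symptomatic positive cases should allow us to attain 70% target sensitivity with precision of 8.98" percent. Deep learning is run on the Primary Analysis Set (5.2), which is these well-to-sick cases.
- **Deep-learning split (4.2.6.3).** The data are divided into "training (e.g., 70% of data), validation (e.g., 10% of data) and test set (e.g., 20% of data"). Only the training/validation division is repeated: "We will replicate the training and validation split three times at the subject level to ensure the results are not biased by single randomization". No replication of the test split is described.
- **Overfitting check (4.2.6, ResNet18 paragraph).** "Cross-validation will be used to determine if the model is overfitting the training data". If it is, "In that case, layers will be removed to reduce the complexity of the model". Sections 4.2.6.3 to 4.2.6.5 specify no k-fold scheme for deep learning.
- **Selection (4.2.6.4, 5.2).** The best deep-learning model is chosen on sensitivity, specificity, balanced accuracy and AUC. Section 4.2.6.4 derives the first three on both the test and the validation sets. Section 5.2 then reports "mean and standard deviation) for classification of sick and well states for the validation set".
- **Final output (4.2.6.4, 4.2.6.5).** The first section describes one final model retrained on the whole training set. The second reports hold-out predictions for three replications.
- **Classical models (4.2.5.1).** "Repeated stratified k-fold cross validation (on the subject level) on the training data will be used to evaluate performance".

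**The concern.** The plan gives its more flexible model family the thinner validation. The deep-learning options listed include ResNet18, VGG16, VGG19, custom networks, a possible long short-term memory layer and two transformer models. Any choice among those fitted rests on three validation sets of about ten people each, and most development cases are never used to judge a model.

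Three things are at stake:

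- whether the model taken to the hold-out is the best of those tried;
- whether the validation results reported in 5.2 are precise enough to interpret, since their standard deviation comes from only three values;
- whether the classical and deep results can be compared, or stacked as 4.3 allows, when they rest on different participants and schemes.

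**Working it through.** **Inputs from the adSAP.** 100 cases and a 70% target sensitivity (4.1); example fractions 70/10/20 and three replications (4.2.6.3).

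**Step 1. The plan's own precision figures.** The SAP says that "for a sensitivity of 70% with 10% margin of error for the 95% confidence interval (i.e., 60% to 80%), 81 cases are required". The normal-approximation formula gives

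n = 1.96² × 0.7 × 0.3 / 0.10² = 80.7, rounded up to 81.

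With 100 cases the half-width is 1.96 × √(0.21/100) = 8.98 points. Both figures reproduce, so the same formula is used below. The SAP gives no corresponding figure for the validation sets.

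**Step 2. Coverage.** Of 100 cases, 20 go to test and 80 remain for development, with 10 in each validation set. If the three sets are drawn independently, the expected number of distinct validated cases is

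80 × (1 − (70/80)³) = 80 × 0.330 = 26.4.

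Simulation gave a mean of 26.4 and a 95% range of 23 to 29. About 54 development cases are never validated. If the sets are kept disjoint, 30 are covered.

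**Step 3. Precision at 70% sensitivity.** With three independent draws, each case is counted w times, where w is binomial (3, 1/8). The expected sum of w² over 80 cases is 80 × [3 × (1/8)(7/8) + (3/8)²] = 37.5, so the effective sample size is 30²/37.5 = 24.

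| Validation scheme | Effective n | 95% half-width |
|---|---|---|
| One split of 10 | 10 | 28.4 points |
| Mean of three splits, independent draws | 24 | 18.3 points |
| Mean of three splits, disjoint | 30 | 16.4 points |
| All 80 validated once | 80 | 10.0 points |

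**Step 4. Dependence on the split alone, given the 80 cases.** For one split the SD is √[(0.21/10) × (70/79)] = 13.6 points. For the mean of three independent splits it is 13.6/√3 = 7.9 points, a 42% reduction.

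**Step 5. Chance of selecting the better model (illustrative).** The documents give no accuracy gap, no correlation between candidates and no number of candidates, so these were assumed and varied. Base accuracy was 70%, with one candidate better by 5 or 10 points. Latent correlation was 0 or 0.5, and the metric was sensitivity or balanced accuracy. There were 6,000 runs per setting, with ties shared. Ranges run over metric and correlation.

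| Candidates (chance rate) | Gap | Three splits of 10 | All 80 validated |
|---|---|---|---|
| 2 (50%) | 5 points | 64-75% | 76-88% |
| 2 (50%) | 10 points | 78-91% | 93-99% |
| 4 (25%) | 5 points | 40-53% | 56-76% |
| 4 (25%) | 10 points | 60-81% | 83-98% |
| 6 (17%) | 5 points | 32-42% | 43-68% |
| 6 (17%) | 10 points | 49-74% | 78-98% |

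The balanced-accuracy runs treat a participant's sick and well classifications as independent, which favours the upper end of each range. Variation from retraining is ignored under both schemes.

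**The case against.** Several points on the other side stand.

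- **The fractions are examples.** The sponsor could choose larger validation sets, and 4.2.6.3 does not say whether the three sets may overlap.
- **The selection contest may be small.** Section 4.2.6 says the network architectures will be chosen on the dimension of the final dataset, and most candidates are optional. Deep learning itself is conditional on the data.
- **Participants give more than one recording.** Sick and well windows can span several days, which helps somewhat. The participant is still the independent unit.
- **The hold-out limits the harm.** Optimism in the winner's validation result does not carry into a clean hold-out test, and Secondary Analysis Sets A and B are used for further testing. The hold-out cannot recover a better model that was passed over, however, and with about 20 cases its own half-width at 70% is 20.1 points. It is clean only if the test metrics in 4.2.6.4 play no part in selection.

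A reader might infer that 4.2.6 and 4.2.6.3 flatly contradict each other. The documents do not support that. Repeated random subject-level splitting can be called a form of cross-validation, and the sentence in 4.2.6 concerns overfitting and the number of layers. The term needs clarifying.

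A reader might also infer that three splits make the choice of architecture close to chance. In every setting tried, the better model was picked about 1.3 to 4.4 times as often as chance would give.

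**Conclusion.** The point holds as one of imprecision. At the example fractions with 100 cases, validation uses about a third of the development cases. It estimates a 70% sensitivity to within about 18 points, where the same 80 cases could give 10. The three replications remove 42% of the split-choice SD; the sentence in 4.2.6.3 promises more than that.

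Selection is unreliable when candidates differ by about 5 points, and more so as candidates are added. No single selection probability can be claimed, because the gap, the correlation and the number of candidates are all assumed. Nor do the documents show that the study will end with an inferior model or understate what voice can do.

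The change is worth making because the better method is already in the SAP for the classical models and costs little.

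**What to change.** 1. In 4.2.6.3, replace the three splits with stratified subject-level k-fold on the development cases, using the same folds as 4.2.5.1. This requires both families to share one development set and one hold-out. Eight folds, for example, train on 70 and validate on 10, which keeps the present sizes.
2. Select the deep-learning model on the pooled out-of-fold predictions only. Amend 4.2.6.4 so that the test set is not used for selection.
3. Retrain one final model on all development cases, test it once on the hold-out, and strike the reference to three replications from 4.2.6.5.
4. State in 4.2.6 that its cross-validation means this scheme.

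Classical and deep models then have out-of-fold predictions on the same participants, for comparison and for any stacking under 4.3. The cost is SAP wording and about 8 fits per candidate instead of 3 for one pass through the folds, with further fits if the k-fold is repeated. No new data are needed.
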